#### **Research objectives:**

### **Primary Objectives:**

The primary objectives are to quantify changes in the following in response to 12 sessions (2x per week for 6 weeks) of using the S-Press device supervised by a Physiotherapist. The primary outcomes are to assess:

- Functional improvements using the 5x sit to stand test.
- Morphological changes, measuring muscle thickness of the Vastus Lateralis and Rectus Femoris muscle using B-Mode ultrasound.
- Any safety issues with *S-Press* use with older users.
- Perceptions of usability of the S-Press with older adult users and care givers.

Short title: S-Press

Sponsor code: JT Rehab-01

IRAS number: 251647

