### Criteria for participant withdrawal

Participants (both NHS staff and in-patients) may voluntarily withdraw from the study at any point. Participants will be informed that their participation is voluntary and that they may withdraw from the study at any time without giving a reason and without it affecting their clinical care or legal rights. Any data provided to that point will be used unless the patient requests otherwise. If the patient requests to have their data withdrawn, all data relating to that participant will be securely destroyed. From a clinical perspective, any in-patient participant that experiences an adverse event will be removed from the study. During exercise sessions, heart rate and blood pressure will be monitored, and where necessary sessions ceased. For blood pressure measures, exercise sessions will be stopped a systolic blood pressure measurement of >210mmHg for men and >190mmHg for women or a decrease of systolic blood pressure >10mmHg from resting values will be considered as stop points (American College of Sports Medicine, Guidelines for exercise testing and prescription, 10th Edition). The occurrence of such event will be classed as criteria for withdrawal from the study on safety grounds.

There is a very small chance of joint injury around the knee or an increase in pain associated with osteoarthritic joints. Knee injury risk will be reduced by the supervision of sessions and individualised set up of the S-Press device. A significant increase in joint pain resulting from using the device will be a withdrawal criterion.

Short title: S-Press

Sponsor code: JT Rehab-01

IRAS number: 251647

Should participant withdrawal occur, this will be followed-up by the chief investigator and documented with the study findings.

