#### **Exercise Sessions**

First, participants will be asked to warm up supervised by the physiotherapist, this will incorporate some low intensity range of movement exercise and light stretching.

Staff participants will set up the patient participant using the S-Press protocol for set up. Patients can remain on the bed or in the chair so will not require transferring or position change by the staff for use.

Short title: S-Press

Sponsor code: JT Rehab-01

IRAS number: 251647

Initial assessment of appropriate resistance level will be examined at the beginning of the first session, by assessing the patient participants 1 repetition max (1RM) level (maximum resistance level ability - Instructions stated in set up protocol).

Participants will then complete 3 sets of 10 repetitions on each leg firstly for the knee extensors and then the knee flexors. The S-Press allows both Concentric and Eccentric muscle actions, so muscle groups are performed independently. A guide of 1 minute's rest will be provided in between sets and legs, although more rest will be allowed if required by the participants. The amount of time per exercise session will be approximately 30 minutes.

Blood pressure and heart rate will be measured before the exercise session begins, mi-way through and again at the end of the session. This is to ensure that there is maintenance of optimal levels of blood pressure and heart rate and monitoring of any adverse effects. These measurements are regularly taken by therapy staff to assess their patients' conditions before and during physical intervention.

Data from the assessments will be analysed using paired t-tests. As this trial is an efficacy and feasibility trial descriptive statistics (mean, standard deviation and % Change) will be calculated. In addition, Cohen's D will be used to determine effect sizes to quantify the magnitude of any differences in variables. A p value of p<0.05 will be used to determine significance, with effect size of <0.2=small; 0.5= moderate; >0.8 large.

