#### **Serious adverse event reporting:**

Potential adverse events that are common to novel physical activity such as delayed muscle soreness, feeling faint as well as temporary increases in heart rate, breathing rate and blood pressures, are planned for within the study and risk minimized with a thorough warm up and cool down with participants as well as supervision throughout the session.

There is a very small chance of joint injury around the knee or an increase in pain associated with osteoarthritic joints. Knee injury risk will be reduced by the supervision of sessions and individualised set up of the S-Press device. A significant increase in joint pain resulting from using the device will be a withdrawal criterion.

Although there is a risk associated with physical activity, numerous studies have shown that physical activity is safe, and beneficial to the health of patients in this environment (Henskens et al., 2018; Kalinowski et al., 2012). The most severe risks associated with physical activity are death or serious cardiac event (Vuori 1986).

Increasing or maintaining skeletal muscle mass has also been shown to increase quality of life and reduce the incidence of MSK injuries caused by trips and falls (Skelton & Beyer 2003).

Participants will be made aware of all the processes involved in data collection stages before the beginning of the study. Individual clinicians will be aware of their medical history and will have upto-date training on first aid and dealing with any adverse events that could potentially occur.

Individual sessions will be postponed or cancelled if an individual is feeling unwell. If the session has started and participants suddenly feel ill whilst performing exercises or they experience tissue viability issues to do with skin integrity or damage caused by the S-Press or signs of cardiac event, then nursing staff will be alerted and session ended. Any adverse event, serious or not will be reported back to nursing staff and reported with the daily log and data collection sheets.

Data will be collected in line with the NIHR guidance on good clinical practice. The PI will ensure the study is carried out in accordance with the protocol (equipment calibrated, facilities suitable and

Short title: S-Press

Sponsor code: JT Rehab-01

IRAS number: 251647

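### Safety is a primary outcome, but the protocol schedules no structured check for the joint pain, skin damage and delayed soreness it names, so these harms may be under-recorded

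*Protocol*

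**What the plan says.** The Protocol's Primary Objectives list "Any safety issues with *S-Press* use with older users" among the primary outcomes, with no measure or time point attached.

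Three harms are then named:

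- **Knee injury or joint pain.** Criteria for participant withdrawal states "There is a very small chance of joint injury around the knee or an increase in pain associated with osteoarthritic joints" and adds "A significant increase in joint pain resulting from using the device will be a withdrawal criterion". Both sentences recur under Serious adverse event reporting.
- **Skin damage.** Serious adverse event reporting has the session ended and nursing staff alerted if, among other things, "they experience tissue viability issues to do with skin integrity or damage caused by the S-Press".
- **Delayed soreness.** The same section opens with "Potential adverse events that are common to novel physical activity such as delayed muscle soreness, feeling faint" and says that such events have been allowed for.

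Exercise Sessions fixes the timed measurements: "Blood pressure and heart rate will be measured before the exercise session begins, mi-way through and again at the end of the session". Their stated purpose is "maintenance of optimal levels of blood pressure and heart rate and monitoring of any adverse effects".

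The assessments described under Physiological Assessments, at baseline and 48-72 hours after the last session, are muscle thickness and the 5x sit to stand.

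For other detection, Serious adverse event reporting provides supervision for the whole of each session and sends every adverse event, whatever its seriousness, to nursing staff and onto the daily log and data collection sheets. The justification for NHS staff involvement says that patients receive ward therapy every day.

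**The concern.** A primary outcome should be collected in the same way for every patient. Here the harms most closely tied to a spring-resisted leg device have no set moment at which anyone must ask or look, while blood pressure and heart rate have three per session. A harm that appears after a session is the most exposed, because the next device session may be days away and no item on that day asks about the interval.

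The joint-pain criterion has a related weakness. An increase needs a starting value, and none is recorded. The word significant is not defined either. Sessions run at four sites, and eligible staff range from physiotherapists to activity co-ordinators, so the criterion may be applied differently from place to place.

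The safety result is meant to support CE marking. A report of no joint, skin or soreness problems carries weight only if the harms were sought and their absence was written down.

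**Working it through.** **1. The plan's own figure.** Sample size justification gives a minimum of 12 and 20% attrition: 12 / (1 - 0.20) = 15, the lower end of the 15-20 target. After attrition, 15 x 0.8 = 12 to 20 x 0.8 = 16 remain. This is reproduced and not in dispute. The safety denominator is everyone exposed, so 15 and 20 are used below.

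**2. What is scheduled for each item.**

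| Item | Timed check | Route into the record |
|---|---|---|
| Blood pressure, heart rate | Before, midway and at end of each session | Measured |
| Knee joint pain | None stated | Supervision, ward contact, log |
| Skin damage | None stated | Session-ending rule, ward contact, log |
| Delayed soreness | None stated | Ward contact, log |

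Over 12 sessions (twice weekly for 6 weeks) this is 3 x 12 = 36 timed blood pressure and heart rate occasions per patient, against 0 for the other three. The 48-72 hour post-test adds no safety item. The interviews are not designed to fill the gap: their preset codes are feasibility, usability and acceptability. These counts show what is timed. They do not show how many harms are missed.

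**3. The joint-pain criterion.** It needs a value before use, a value after use and a definition of a significant difference. The protocol provides none of the three.

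**4. The removal rule.** Criteria for participant withdrawal says that any in-patient who has an adverse event leaves the study. The same section then makes joint pain a criterion only when the increase is significant. Serious adverse event reporting lists delayed soreness as a potential adverse event that the study allows for. Read literally, the first rule makes the second redundant and removes patients for an effect that the third passage anticipates.

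**5. What incomplete detection could do (illustration only).** The documents give no event rate and no detection rate. Assume a true proportion p of patients with a given harm, a probability s that an affected patient is recorded, and independence between patients. Then

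P(at least one recorded) = 1 - (1 - p x s)^n.

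For example, with n = 15, p = 0.10 and s = 0.5: 1 - 0.95^15 = 0.54.

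| n | p | s = 1 | s = 0.75 | s = 0.5 | s = 0.25 |
|---|---|---|---|---|---|
| 15 | 0.05 | 0.54 | 0.44 | 0.32 | 0.17 |
| 15 | 0.10 | 0.79 | 0.69 | 0.54 | 0.32 |
| 15 | 0.20 | 0.96 | 0.91 | 0.79 | 0.54 |
| 20 | 0.05 | 0.64 | 0.53 | 0.40 | 0.22 |
| 20 | 0.10 | 0.88 | 0.79 | 0.64 | 0.40 |
| 20 | 0.20 | 0.99 | 0.96 | 0.88 | 0.64 |

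If no event is recorded, the one-sided 95% upper limit is 1 - 0.05^(1/n): 18.1% for n = 15 and 13.9% for n = 20. These limits hold only with complete detection. If s were 0.5 they would be 18.1 / 0.5 = 36.2% and 13.9 / 0.5 = 27.8%.

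**The case against.** The strongest reply is that these harms are being watched for. Every session is supervised, skin damage ends a session, the stated purpose of the session readings includes adverse effects in general, and all adverse events go to nursing staff and the log. The participants are in-patients with daily therapy contact. The log and data sheets are not shown and may contain prompts, and the protocol itself rates the chance of joint harm as very small.

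Most of this stands, and it rules out three stronger readings:

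- A reader might infer that monitoring consists of blood pressure and heart rate alone, or that nobody looks for the other harms. That is true only of timed measurements.
- A reader might infer that the safety outcome is bound to under-count. No detection rate can be derived from the documents, so under-recording is a risk and not a demonstrated result.
- A reader might take all three harms as particular to the device. The protocol describes delayed soreness as common to any new physical activity.

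What the reply does not supply is a requirement to ask. Supervision covers about 30 minutes twice a week and cannot see an effect that begins later. The log provision says where an event goes once known. Daily therapy carries no stated safety question, though it shows that one would be easy to put. A statistical analysis plan could not recover pain scores or skin checks that were never collected.

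**Conclusion.** The point holds as a weakness in how a primary outcome is collected. No scheduled, structured enquiry is set for joint pain, skin damage or delayed soreness, and the joint-pain criterion has no recorded baseline. These harms may be under-recorded, most of all those that appear after a session.

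The size of any under-count cannot be computed from the documents. Under the assumed values above, halving detection at a 10% true rate lowers the chance of seeing even one case from 0.79 to 0.54 with 15 patients, and from 0.88 to 0.64 with 20. The conclusion assumes that the unseen log and sheets do not already contain such prompts. If they do, the protocol need only say so.

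The withdrawal and adverse event passages also conflict, whatever the log contains. This should be corrected before recruitment, though it does not undermine the design.

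**What to change.** **First, reconcile the passages.** The sponsor must reconcile the removal of any in-patient with an adverse event, the separate joint-pain criterion, and the treatment of delayed soreness as a potential event that the study allows for. The clinical rule and any threshold are for the sponsor to set.

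**Then add three items to the existing session sheet:**

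- a knee pain score before and after each session, starting at familiarisation so that a value before device use exists;
- soreness or any other problem since the last session, yes or no;
- skin of the supported leg intact, yes or no.

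Repeat them once at the 48-72 hour post-test so that the period after session 12 is covered. Record nil findings as well as positive ones. Report, for each harm, patients affected over patients exposed, including those who leave early.

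**Cost.** An estimated minute of staff time per occasion: 12 sessions plus familiarisation and post-test is about 14 minutes per patient, with a revised data sheet and no new visit, staff or equipment. More minor events will be recorded. If the passages are not reconciled first, the soreness item could itself trigger removals from a sample of 15-20 with a stated minimum of 12.

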## Description of the generally recognised medical diagnosis for investigational testing

The generally recognised medical diagnosis of muscle weakening due to the de-conditioning effect, post injury or illness, and sarcopenia and natural age-related muscle weakening is being proposed for the study.

### Proposed post-market clinical follow-up plan:

There is no specific post-market follow-up set up yet due to this being a preliminary efficacy and feasibility study.

On-going evaluation of products on the market will be performed through planned customer feedback and customer services. Only through constant systematic market surveillance (postmarket surveillance) can JT Rehab guarantee that the S-Press provides the promised benefit to patients as well as the lack of any unrestrained risks.

If "regular market surveillance" does not provide sufficient data, post-market clinical follow-up studies regarding the manufacturer may become necessary.

To meet MDR requirements, JT Rehab will design and run PMCF studies with three major goals in mind:

- Confirming device safety and clinical performance
- Ensuring continued acceptability of identified risks
- Detecting emerging risks based on factual evidence

## Physiological Assessments (Quantitative Data)

These assessments will be conducted at baseline (start) and at the end of the intervention period (6 weeks). Post testing will be conducted 48-72 hours post final exercise session to allow for any fluid changes within the muscle to subside and minimise fatigue of participants. There will be a familiarisation session for all participants prior to completing the baseline assessments to minimise any learning effects of the assessments.

Short title: S-Press

Sponsor code: JT Rehab-01

IRAS number: 251647

#### **Familiarisation**

Following obtaining informed consent, participants will be provided with an opportunity to have a practice attempt/s at each of the assessments and also the exercise session. For the exercise sessions this will be used to identify the starting point in terms of resistance for each individual. All exercise sessions and assessments will be performed on the ward minimising extraneous travel costs for participants.

The physiological assessments are as follows:

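### S-Press practice precedes baseline with no exercise-free interval required, while post-testing must wait 48-72 hours, so like-for-like measurement is not guaranteed

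*Protocol*

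**What the plan says.** The Physiological Assessments section of the protocol fixes the order of events: "There will be a familiarisation session for all participants prior to completing the baseline assessments". Its stated purpose is to limit learning effects in the assessments. The Familiarisation section then gives the content of that session as "practice attempt/s at each of the assessments and also the exercise session", and adds a second use for the exercise part: "For the exercise sessions this will be used to identify the starting point in terms of resistance for each individual".

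For the other end of the trial the Physiological Assessments section sets a waiting time and gives the reason: "Post testing will be conducted 48-72 hours post final exercise session to allow for any fluid changes within the muscle to subside", and also to limit fatigue. No section sets a corresponding interval between familiarisation and baseline.

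The Exercise Sessions section places the setting of resistance elsewhere: "Initial assessment of appropriate resistance level will be examined at the beginning of the first session, by assessing the patient participants 1 repetition max". The same section specifies the analysis: "Data from the assessments will be analysed using paired t-tests". The design is single-arm (Type of study design). The 5x sit to stand and the ultrasound thickness of two thigh muscles are both listed under Primary Objectives.

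**The concern.** The protocol recognises that recent S-Press work can disturb both quantitative primary measurements, through muscle fluid and through fatigue. It protects only the second measurement from this. S-Press work also comes before the first one, at an unstated distance in time and an unstated load.

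In a single-arm pre-post comparison a shift at baseline passes straight into the estimated change, because no control group shares it. Blinded reading of the images does not remove real swelling, and rest between sit-to-stand attempts does not address the effect of earlier exercise.

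The two possible shifts act in opposite directions:

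- **Sit to stand.** A tired or sore patient is slower at baseline, so recovery alone looks like improvement and favours the device.
- **Muscle thickness.** A muscle holding extra fluid is thicker at baseline, so growth is understated and the result works against the device.

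The protocol itself makes some residual effect plausible. It notes that "The S-Press allows both Concentric and Eccentric muscle actions", and its safety section lists potential adverse events "common to novel physical activity such as delayed muscle soreness". The data are intended to support CE marking.

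**Working it through.** **Step 1: the two measurement points side by side.**

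| | Baseline | Post-test |
|---|---|---|
| Preceding S-Press exercise | Practice at familiarisation, also used to find the starting resistance | Last of 12 training sessions |
| Amount | Not stated | 3 sets x 10 repetitions x 2 legs x 2 muscle groups = 120 repetitions |
| Required interval before testing | None stated | 48-72 hours |

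The text permits baseline on the same day as the practice. It equally permits a gap of several days.

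**Step 2: is the pre-baseline resistance step needed?** Familiarisation is said to identify the starting resistance. The Exercise Sessions section has the level assessed by 1RM at the start of the first session, which I read as the first of the 12 training sessions and so after baseline. The first session can supply the starting level without the earlier step. The stated reason for familiarising before baseline, learning effects in the assessments, does not require S-Press exercise either.

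**Step 3: number of completers.** Sample size justification: minimum 12, attrition 20%, recruitment 15-20. Check: 12 / (1 - 0.20) = 15, which reproduces the lower end of the target. Completers: 15 x 0.8 = 12 and 20 x 0.8 = 16.

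**Step 4: illustration of what a shift could do.** The protocol gives no size for a carry-over effect. I assume a mean shift b of 0.1, 0.2 or 0.3 SD of the change score across the whole sample. The test is a paired t-test at 5%, taken as two-sided because the protocol does not say. Critical values are t = 2.201 (n = 12, 11 df) and 2.131 (n = 16, 15 df).

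- Sit to stand with no true effect: the probability of a significant favourable result is the upper tail of a noncentral t with noncentrality b x sqrt(n). Example: n = 16, b = 0.3 gives 0.3 x 4 = 1.2.
- Muscle thickness with an assumed true d = 0.8: power uses noncentrality (0.8 - b) x sqrt(n). Example: n = 12, b = 0.2 gives 0.6 x 3.464 = 2.078. The protocol does not state 0.8 as an expected effect; the value appears there only as the threshold for a large one.

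| Assumed shift b | False favourable sit-to-stand result, n = 12 | n = 16 | Thickness power at d = 0.8, n = 12 | n = 16 |
|---|---|---|---|---|
| 0 | 2.5% | 2.5% | 71.4% | 84.8% |
| 0.1 | 5.0% | 5.7% | 59.9% | 74.5% |
| 0.2 | 9.3% | 11.3% | 47.5% | 61.2% |
| 0.3 | 15.6% | 20.2% | 35.3% | 46.5% |

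The first row is what applies if every site leaves a sufficient gap. The other rows show how sensitive a small paired comparison is; they do not estimate the bias in this trial.

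**The case against.** A reader might infer that baseline is taken straight after S-Press exercise with no recovery, and that the two time points are therefore measured under different conditions. The documents do not support this. They say only that familiarisation comes first. The interval is unstated, and sites may leave 48 hours or more, in which case nothing is distorted.

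A reader might also treat the practice as equivalent to a training session. That does not hold either. The 48-72 hour rule follows a full session, whereas familiarisation offers one or more practice attempts at an unstated load. The only maximal effort the protocol describes, the 1RM, belongs to the first session. The two statements on resistance can also be reconciled: practice suggests a starting point and 1RM then sets the level. The set-up protocol that the text refers to for 1RM is not at hand and may say more.

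Three further objections have weight:

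- The mechanisms belong to different timings. Fluid and acute fatigue matter if baseline follows soon after practice; delayed soreness matters later. Neither can be dated or sized from the document.
- The figures above depend on assumed inputs and cannot by themselves show that the problem is serious.
- The trial is an uncontrolled feasibility study in inpatients who already receive daily therapy. Natural recovery and usual physiotherapy confound any pre-post change, so even with a perfect baseline the nominal 2.5% does not describe the risk of wrongly crediting the device.

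What remains is the one-sided rule. The protocol fixes the visit order and the measurement conditions itself, and it places S-Press loading before baseline without the safeguard it considers necessary afterwards. Other sources of confounding are no reason to leave in one that can be removed by rewording.

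**Conclusion.** The point holds in limited form. S-Press practice, used to find the starting resistance, precedes baseline without any required exercise-free interval, while post-testing has one for stated reasons that apply equally to baseline. Equal measurement conditions are therefore not guaranteed for two primary outcomes in a single-arm paired analysis. Any residual fatigue would flatter the sit-to-stand result, and any residual fluid would hide muscle growth.

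The size cannot be obtained from the protocol. It is probably smaller than the effect of a full session, and it is nil where the gap is 48 hours or more. The error and power figures rest on an assumed 0.1-0.3 SD shift, an assumed d of 0.8, 12-16 completers and a two-sided test, and are illustrative only. Separately, the pre-baseline resistance step duplicates the 1RM assessment at the first session. This is a cheap improvement worth making; it does not show that the results will be biased.

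**What to change.** **Preferred.** Amend the Physiological Assessments and Familiarisation sections along these lines: *Before baseline, participants practise the assessments only. S-Press practice takes place after the baseline assessments. The starting resistance is set once, by 1RM, at the beginning of the first session.* This keeps the practice that limits learning effects, removes S-Press loading from the period before baseline, and leaves one statement of when resistance is set. It needs no extra visit. The first session may run slightly longer than the planned 30 minutes or so, unless the practice is done after baseline on the same day.

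**Alternative, if S-Press practice must stay before baseline.** Require at least 48 hours between it and the baseline assessments, and record the dates of both. This may delay baseline by about two days where sites do not already leave that gap. The Duration of study section equates the six-week programme with the length of the ward stay, so a delay could cost some post-tests through discharge. That is a reason to prefer the first option.
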